16 ADMINISTRATIVE, ETHICAL, REGULATORY CONSIDERATIONS

16.1	Protocol Amendments
16.2	Institutional Review Boards and Independent Ethics Committees
16.3	Informed Consent Form
16.4	Publications
16.5	Investigator Responsibilities

LIST OF ABBREVIATIONS

AE	Adverse event
ADLD	Adductor laryngeal dystonia
Botox	OnabotulinumtoxinA
CAPE-V	Consensus Auditory-Perceptual Evaluation of Voice
CFR	Code of Federal Regulations
CPIB-10	Communicative Participation Item Bank-10
CRF	Case report form
DAXI	DaxibotulinumtoxinA
DMC	Data Monitoring Committee
EAT-10	Eating Assessment Tool-10
FDA	Food and Drug Administration
GCP	Good Clinical Practice
HIPAA	Health Insurance Portability and Accountability Act of 1996
ICF	Informed consent form
ICH	International Conference on Harmonisation
IEC	Independent Ethics Committee
IRB	Institutional Review Board
LD	Laryngeal dystonia
OMNI-VES	OMNI Vocal Effort Scale
PI	Principal Investigator
PROMs	Patient Reported Outcome Measures
SAE	Serious adverse experience

VAS	Visual Analog Scale
VHI-10	Voice Handicap Index-10

PROTOCOL SYNOPSIS

TITLE	A single-arm, open-label, dose-escalation clinical trial of DaxibotulinumtoxinA for treatment of adductor laryngeal dystonia
SPONSOR	[name] M.D.
FUNDING ORGANIZATION	Departmental funding from the UCSF Department of Otolaryngology
NUMBER OF SITES	1
RATIONALE	
Laryngeal dystonia (LD) is a neurologic condition causing aberrant contraction of the laryngeal musculature, leading to abnormal voicing during speech. The three types (adductor, abductor, and mixed) affect varying muscle groups which produce characteristic voice patterns. The vast majority of patients with SD have adductor type, which impacts the lateral cricoarytenoid and thyroarytenoid muscle complex. While many treatment modalities have been investigated, the most efficacious treatment is botulinum toxin injection to these muscle groups, performed transcervically with or without electromyography (EMG) guidance. Patients undergoing this treatment typically require re-injection every three months. Due to its specialized nature, the laryngeal injections are not performed routinely outside of academic medical centers; thus, patients may come from a distance to receive this treatment. Both due to the significant impact on voice quality when the injections

	
wear off and the sometimes challenging access to treatment, a longer acting agent is desire.
 
Injectable daxibotulinumtoxinA (DAXI, Revance Therapeutics Inc., Newark, CA) is a FDA-approved botulinum toxin type A indicated for the treatment of glabellar lines. It has been shown in large clinical trials to provide safe, effective treatment for cervical dystonia and may offer longer-lasting results when compared with onabotulinumtoxinA.
 
Thus, a study examining the effect of DAXI for patients with adductor laryngeal dystonia (ADLD) is proposed. This study aims to assess the efficacy of DAXI for transcervical laryngeal injection in patients with adductor laryngeal dystonia.

STUDY DESIGN	A single-arm, open-label, dose-escalation phase 4 study.
PRIMARY OBJECTIVE	Determine the efficacy of DAXI for treatment of ADLD.
SECONDARY OBJECTIVES	Compare duration of benefit between DAXI and BotoxA.
NUMBER OF SUBJECTS	20

SUBJECT SELECTION CRITERIA	
Inclusion Criteria:
 
Age ≥ 18
 
Diagnosis of adductor laryngeal dystonia (ADLD)
 
Previous successful treatment with BotoxA and stabilized dose for the last 3 treatments
 
Acceptable form of birth control for females of childbearing potential.
 
Women of childbearing age must have a negative pregnancy test
 
Female participants of childbearing potential may be enrolled in the study if the participant fulfills all the inclusion criteria listed in the subject selection section below.
 
Exclusion Criteria:
 
Age < 18
 
Other neurologic conditions (ALS, Parkinson's disease, essential tremor, Meige syndrome, etc.)
 
Pregnant, breastfeeding, or unwilling to practice birth control during participation in the study.
 
Presence of a condition or abnormality that in the opinion of the Investigator would compromise the safety of the patient or the quality of the data.
 
Naive from other types of Botox for 6 months including BotoxA

TEST PRODUCT, DOSE, AND ROUTE OF ADMINISTRATION	
Open-label dose of DAXI injected at either 0.625, 1.25, or 2.5 units. Dosage will be determined by subject's previous stabilized Botox dosage.

CONTROL PRODUCT, DOSE AND ROUTE OF ADMINISTRATION	N/A
DURATION OF SUBJECT PARTICIPATION AND DURATION OF STUDY	Subjects will be in the study for up to 36 weeks. Total time for recruitment and completion of the study will be up to 2 years.
CONCOMMITANT MEDICATIONS	Allowed: all Prohibited: Other forms of Botox
EFFICACY EVALUATIONS	Validated laryngology PROMs, voice analysis via mobile app (voice recording sample), duration of effect
PRIMARY ENDPOINT	Efficacy, measured quantitatively through VHI-10 questionnaires
SECONDARY ENDPOINTS	Duration of benefit, assessed qualitatively through phone call surveys
OTHER EVALUATIONS	Participant Questionnaires CPIB-10 OMNI-VES EAT-10

	Clinician Scales Unified spasmodic dysphonia rating scale (USDRS) Phonalyze
SAFETY EVALUATIONS	Incidence of adverse events
PLANNED INTERIM ANALYSES	When approximately 50% of patients have completed the study's initial injection, an interim analysis for safety will be conducted.
STATISTICS Primary Analysis Plan	Safety profile including AE and SAEs will be reported. Simple descriptive statistics will be used to summarize toxicities in terms of type, severity and minimum or maximum values for laboratory measures, time of onset, duration, and reversibility or outcome. Tables will be created to summarize these toxicities and side effects. Safety Analyses will be performed on Safety Analysis Set.
Rationale for Number of Subjects	A sample size of 20 will provide 80% power to detect a difference of 6.6 at a significance threshold (alpha) of 0.05.

1 BACKGROUND

Approximately 50,000 people in North America have a diagnosis of adductor laryngeal dystonia (ADLD). Laryngeal dystonia (LD) is a neurologic condition causing aberrant contraction of the laryngeal musculature, leading to abnormal voicing during speech. The three types (adductor, abductor, and mixed) affect varying muscle groups which produce characteristic voice patterns. The vast majority of patients with SD have adductor type, which impacts the lateral cricoarytenoid and thyroarytenoid muscle complex. While many treatment modalities have been investigated, the most efficacious treatment is botulinum toxin injection to these muscle groups, performed transcervically with or without electromyography (EMG) guidance. Patients undergoing this treatment typically require re-injection every three months. Due to its specialized nature, the laryngeal injections are not performed routinely outside of academic medical centers; thus, patients may come from a distance to receive this treatment. Both due to the significant impact on voice quality when the injections wear off and the sometimes challenging access to treatment, a longer acting agent is desired.

1.1 Overview of Non-Clinical Studies

An animal model has demonstrated reduced diffusion of the neurotoxin with this formulation which may account for its longer duration of effect. DAXI can be formulated without the use of human serum albumin ensuring its stability at room temperature before reconstitution.

1.2 Overview of Clinical Studies

Injectable daxibotulinumtoxinA (DAXI, Revance Therapeutics Inc., Newark, CA) has received FDA approval for treatment of glabellar lines and has been shown in large clinical trials to provide safe, effective treatment for cervical dystonia. DAXI may offer a longer-lasting result when compared with onabotulinumtoxin.

2 STUDY RATIONALE

This study aims to assess the efficacy of DAXI for transcervical laryngeal injection in patients with adductor laryngeal dystonia. Secondly, this study aims to assess whether DAXI provides longer clinical benefit than BotoxA for treatment of ADLD.

2.1 Risk / Benefit Assessment

Risks are mitigated through the use of fellowship-trained laryngologists who are experts at this type of injection.

Possible Risks: There are risks to taking part in any research study. Some of the most likely risks of participation in this study include:

- Having no effect on voice
- Requiring multiple injections
- Injection site pain or discomfort

There are also rare but serious risks of participation, like:

- *Difficulty swallowing, possibly requiring a temporary feeding tube*
- *Difficulty breathing, possibly requiring hospitalization*

Possible Benefits:

- Participants may benefit from participating in the study, but this cannot be guaranteed. When looking at previous trials with a different indication, DAXI provided a longer-lasting effect than traditional Botox.

The potential benefits may outweigh the risks as DAXI may ultimately decrease frequency of injection, while maintaining similar risk to Botox injection.

3 STUDY OBJECTIVES

3.1 Primary Objective

Evaluate efficacy of botulinum toxin A neurotoxin, daxibotulinumtoxinA (DAXI) among ADLD subject population

3.2 Secondary Objectives

Determine duration of clinical benefit to assess whether DAXI may provide longer clinical benefit than BotoxA for treatment of ADLD

4 STUDY DESIGN

4.1 Study Overview

This is a single-center, open-label, dose-escalation trial. 20 subjects are planned. Each subject will be administered a single dose of DAXI. If the subject does not achieve the desired self-reported voice improvement, at 1 week post injection an additional dose of DAXI will be administered.

Screening data will be reviewed to determine subject eligibility. Subjects who meet all inclusion criteria and none of the exclusion criteria will be entered into the study.

The following treatment regimens will be used:

- Injection of DAXI at the following doses: 0.625, 1.25, 2.5 units depending on subject's current standard dose of Botox.

Total duration of subject participation will be 36 weeks. Total duration of recruitment and completion of all procedures of the study is expected to be up to 2 years.

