7.4 Supply of Study Drug at the Site

7.4.1 Dosage/Dosage Regimen

Subject's Current* BotoxA Dose	DAXI Dose 1	DAXI Dose 2
-----------------------------------	-------------	-------------

0.625 units unilateral	0.625 unit	0.625 unit
1.25 units unilateral	1.25 units	1.25 units
2.5 units unilateral	2.5 units	2.5 units
0.625 units bilateral	0.625 unit	0.625 unit (contralateral)
1.25 units bilateral	1.25 units	1.25 units (contralateral)
2.5 units bilateral	2.5 units	2.5 units (contralateral)

*Current is defined as the average of subject's last 3 injections

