9.3 Visit 2 (Phone Call, Day 5)

1. Phone call to assess clinical improvement
2. Ensure there is absence of dysphagia (using EAT-10 questionnaire), no injection site issue, or other adverse events using safety survey

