9.4 Visit 3 (Optional Clinic Visit, Day 7-14)

1. Additional DAXI can be administered in office if the 1st injection does not have desired clinical effect
2. Injection occurs on same side if normally unilateral, or on opposite side if bilateral

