APPENDIX 4. SAFETY SURVEY

- Pain, swelling or bruising at the injection site
- Headache
- Flu-like symptoms
- Trouble speaking or swallowing
- Breathing problems
- Cough
- Hoarseness

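### The second DAXI dose depends only on inadequate effect: no swallowing and breathing check has to be done, or be clear, before it is given

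*Combined protocol and SAP*

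**What the plan says.** Two sections govern the second dose.

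- Section 4.1: "If the subject does not achieve the desired self-reported voice improvement, at 1 week post injection an additional dose of DAXI will be administered". The trigger is the subject's own report of voice, and the wording is mandatory.
- Section 9.4 (Visit 3, optional, Day 7-14): "Additional DAXI can be administered in office if the 1st injection does not have desired clinical effect". The trigger is clinical effect, and the wording is permissive. On side it adds: "Injection occurs on same side if normally unilateral, or on opposite side if bilateral".

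The table in 7.4.1 makes dose 2 equal to dose 1 in every row. Section 7.4.3 speaks of a second dose being required but does not define when.

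The swallowing check sits in 9.3, at the Day 5 phone call: "Ensure there is absence of dysphagia (using EAT-10 questionnaire), no injection site issue, or other adverse events using safety survey". That section does not say what follows for Visit 3 if the call is missed or a problem is found. At Visit 3, Appendix 1 marks only the injection and the USDRS, and 9.4 lists no EAT-10 or safety survey either.

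Section 2.1 names the uncommon serious risks: "Difficulty swallowing, possibly requiring a temporary feeding tube" and "Difficulty breathing, possibly requiring hospitalization".

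**The concern.** The second dose is the only step at which a subject's exposure is raised within the trial. It comes within two weeks of the first dose, and the risks named in 2.1 are ones that more toxin could worsen. A reader who follows 4.1 to the letter would re-inject a subject whose voice has not improved enough, even if that subject reported trouble swallowing on Day 5 or was never reached by phone. The plan already collects the information needed to avoid this but does not connect it to the dosing decision.

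The matter is subject safety. It does not touch the paired t-test of VHI-10 at 8 weeks or the sample size.

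**Working it through.** The point rests on the text, supported by day arithmetic. The plan gives no figure of its own for it.

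**1. Is there a safety condition anywhere?**

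| Place | Condition for the second dose | Safety condition |
|---|---|---|
| 4.1 | Inadequate self-reported voice improvement | None |
| 7.4.1 | None (dose only) | None |
| 7.4.3 | That a second dose is required (not defined) | None |
| 9.3 | Not mentioned; Day 5 screen for dysphagia and other AEs | No stated consequence |
| 9.4 | Lack of desired clinical effect | None |
| Appendix 1, Visit 3 | None | No EAT-10; no safety-survey row at any visit |

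**2. Age of the latest EAT-10 at the second injection.** Inputs: Visit 2 on Day 5; Visit 3 on Day 7-14.

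- Nominal schedule: 7 − 5 = 2 days to 14 − 5 = 9 days.
- With the ±2 days that Appendix 1 attaches to both visits, Visit 2 is Day 3-7 and Visit 3 is Day 5-16. The range is then 5 − 7 = −2 days to 16 − 3 = 13 days. A negative value means that the injection comes before the call.

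**3. How often can the order reverse?** There are 5 × 12 = 60 allowed day pairs. The injection precedes the call in three: (Visit 3, Visit 2) = (5,6), (5,7) and (6,7). Three more fall on the same day (5, 6 or 7). If Visit 3 is held to Day 7-14 there are 5 × 8 = 40 pairs, with none reversed and one on the same day (Day 7). These are counts of permitted combinations, not probabilities. Reversal is a corner case.

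**4. Next scheduled EAT-10 after a second dose.** Section 9.5 counts Visit 4 from the most recent injection. A re-dosed subject therefore reaches it on Day 7 + 14 = 21 to Day 14 + 14 = 28. The EAT-10 values around the second injection are then at Day 5 and Day 21-28, a gap of 16 to 23 days.

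**5. Units given.** In a subject always treated on one side, 7.4.1 and 9.4 give an equal second dose on that side: 0.625 + 0.625 = 1.25, 1.25 + 1.25 = 2.5, or 2.5 + 2.5 = 5.0 units. The last is the row "2.5 units unilateral". Usually bilateral subjects receive the second dose on the other side, so the concern is smaller for them.

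**6. Which instrument?** The survey item "Trouble speaking or swallowing" in Appendix 4 joins a symptom of the disease to the safety signal, so the EAT-10 is the specific swallowing measure. The survey has its own item on breathing. Both are needed.

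**7. Power.** For n = 20, difference 6.6, SD 10 and two-sided alpha 0.05, the noncentrality is 6.6/10 × √20 = 2.95 on 19 degrees of freedom. Power is 79.9%, which agrees with the stated 80%. The re-dosing rule enters none of these inputs.

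**The case against.** The best defence is that the check is already there in practice. The Day 5 call is a scheduled visit, not an optional one, and Visit 1 ends by booking it. The same call assesses improvement, so the contact that identifies a subject needing more toxin also screens for dysphagia. Section 10.1 has the investigator ask about AEs at each visit, which includes Visit 3. Section 9.4 permits the dose and does not require it, 11.1 lets the investigator stop treatment for an AE, and 2.1 relies on experienced laryngologists. Appendix 1 is also weak evidence of omission: it leaves out the EAT-10 at Visits 5-10 although 9.6 requires it.

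Most of this stands, and it limits the size of the point. It shows intent and partial protection. It does not supply a rule: 4.1 is still mandatory on effect alone, and no section says that an abnormal or missed Day 5 check delays or stops the dose. Section 9.4 confirms, independently of Appendix 1, that no EAT-10 is planned at Visit 3.

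Three stronger readings might be inferred, and the documents do not support them.

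- *The timings in 4.1 and 9.4 conflict.* One week lies inside Day 7-14. The overview is narrower than the visit section but does not contradict it.
- *Every usually unilateral subject gets twice the usual dose on the same side.* For alternating-side subjects, 7.4.3 continues the alternating sequence while 9.4 says same side, so their second side is unsettled. The documents also state no potency equivalence between DAXI and BotoxA units.
- *Safety findings could wait for the team meeting in section 13.* That committee is the investigator team itself at a single site. Nothing suggests that a Day 5 finding reaches the clinician only through the meeting.

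**Conclusion.** The point holds as a modest safety gap that should be fixed. As written, the plan directs a second dose on inadequate self-reported effect and does not require a completed or clear swallowing and breathing check first. On the nominal schedule the EAT-10 is 2 to 9 days old at re-dosing, and with the visit windows read literally it can be up to 13 days old or not yet done.

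The conclusion rests on the absence of any linking rule in 4.1, 7.4.1, 7.4.3, 9.3, 9.4 and Appendix 1. The day ranges assume that the ±2 days applies to Visit 2 and to both ends of the Visit 3 range. The documents do not say what share of subjects is expected to be re-dosed, so the number exposed to the gap cannot be estimated. The primary analysis and its power are unaffected.

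**What to change.** Put one rule in both 4.1 and 9.4, replacing the mandatory wording in 4.1:

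> A second dose may be administered at Day 7-14, not before Day 7, if voice improvement is insufficient and, on the day of and before the injection, the EAT-10 and safety survey have been completed and reviewed by the investigator. The second dose is withheld if there is new or worsened swallowing difficulty compared with the screening EAT-10, or new breathing difficulty.

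In Appendix 1, mark the EAT-10 at Visit 3 as done before the injection, and add a safety-survey row, since none exists.

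The check should be made on the day for every re-dosed subject, not only when the Day 5 call was missed. Otherwise a clear result up to 9 days old (13 with the windows) would still pass.

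The cost is wording in two sections and one table. No new visit or instrument is needed: the EAT-10, including its screening value, and the safety survey are already in the plan. The downsides are a few minutes in clinic, no second injections on Day 5-6 or Day 15-16, and some second doses withheld.

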5 CRITERIA FOR EVALUATION

5.1 Primary Efficacy Endpoint

The primary efficacy endpoint is the difference in VHI-10 scores at 8 weeks after injection with DAXI. VHI-10 questionnaires will be given at baseline, day 14, then monthly.

5.2 Secondary Efficacy Endpoints

The secondary endpoint is duration of benefit, assessed by median time to baseline VHI-10 after treatment with DAXI and via phone call surveys. VHI-10 questionnaires will be given at baseline, day 14, then monthly until loss of benefit. Phone calls will be conducted at day 5, day 14, then monthly until loss of benefit.

5.3 Safety Evaluations

In the event of an adverse event, the study team will notify the medical monitor.

5.4 Other Evaluations

Participant Questionnaires

- CPIB-10
- OMNI-VES
- EAT-10

Clinician scales

- USDRS
- Phonalyze

SUBJECT SELECTION

5.5 Study Population

Participants with a diagnosis of adductor laryngeal dystonia who meet the inclusion and none of the exclusion criteria will be eligible for participation in this study. Participants will be recruited from the UCSF Voice and Swallowing Center and the National Spasmodic Dysphonia Association community.

5.6 Inclusion Criteria

- Age ≥ 18
- Diagnosis of adductor laryngeal dystonia
- Previous successful treatment with BotoxA and stabilized dose for the last 3 treatments
- Female participants of childbearing potential may be enrolled in the study if the participant fulfills all the following criteria:
 - Has a negative pregnancy test at Visit 1, Day 0.
 - Has practiced adequate contraception or has abstained from all activities that could result in pregnancy for at least 30 days prior to the injection (Day 1).
 - Has agreed to continue adequate contraception through 3 months following the injection (Day 90).
 - Is not currently breastfeeding.

- Adequate female contraception is defined as consistent and correct use of a Food and Drug Administration (FDA) approved contraceptive method in accordance with the product label. For example:
 - Barrier method (such as condoms, diaphragm, or cervical cap) used in conjunction with spermicide
 - Intrauterine device
 - Prescription hormonal contraceptive taken or administered via oral (pill), transdermal (patch), subdermal, or IM route
 - Sterilization of a female participant's monogamous male partner prior to entry into the study
 - Note: periodic abstinence (e.g. calendar, ovulation, post-ovulation methods) and withdrawal are not acceptable methods of contraception.

5.7 Exclusion Criteria

- Age <18
- Other neurologic conditions (ALS, Parkinson's disease, essential tremor, Meige syndrome, etc.)
- Pregnant, breastfeeding, or unwilling to practice birth control during participation in the study.
- Presence of a condition or abnormality that in the opinion of the Investigator would compromise the safety of the patient or the quality of the data.
- Naive from other types of Botox for 6 months including BotoxA

6 CONCURRENT MEDICATIONS

All currently prescribed medications are allowed

6.1 Allowed Medications and Treatments

Standard therapy for other conditions is allowed except for treatments noted in the exclusion criteria described above and as noted in the prohibited medications section below.

6.2 Prohibited Medications and Treatments

The following medications are prohibited during the study and administration will be considered a protocol violation.

- Naive from other types of Botox for 6 months including BotoxA

7 STUDY TREATMENTS

7.1 Method of Assigning Subjects to Treatment Groups

N/A (open-label study).

7.2 Blinding

N/A (open-label study).

7.3 Formulation of Test and Control Products

7.3.1 Formulation of Test Product

Injectable daxibotulinumtoxinA (DAXI, Revance Therapeutics Inc., Newark, CA) is a FDA-approved botulinum toxin type A indicated for the treatment of glabellar lines. It has been shown in large clinical trials to provide safe, effective treatment for cervical dystonia and may offer longer-lasting results when compared with onabotulinumtoxinA. DAXI will be reconstituted using sterile saline into 1mL syringes at the desired dosage similar to clinical care for Botox.

